5.7. Concomitant Medications, Procedures, and Supportive Care Guidelines

No restrictions on supportive care, except as noted in Section 3.1.3. (Lifestyle Considerations), Section 5.7.1. (Concomitant Medications to Avoid), Section 5.7.2. (Prohibited Concomitant Medications and Procedures), and Section 5.7.3. (Permitted Concomitant Medications).

5.7.1. Concomitant Medications to Avoid

Avoid with nirogacestat:

- CYP3A4 substrates with a narrow therapeutic index
 - Should be avoided if possible, and
 - If co-administration is unavoidable, the subject should be monitored closely for toxicity, and investigator should consider reducing or titrating the dose of the substrate as necessary.
- Gastric acid reducing agents, such as proton pump inhibitors
 - Should be avoided if a reasonable alternative is available; and
 - If administration is necessary, should be administered 4 hours following dosing with nirogacestat.

5.7.2. Prohibited Concomitant Medications and Procedures. See also Section 3.1.3. Lifestyle Considerations

- Other investigational anti-cancer therapies
- Anti-cancer surgery
- Definitive radiation (treatment with intent to cure) is not allowed. However, palliative radiation is allowed.
- Strong and moderate CYP3A4 inhibitors and strong CYP3A4 inducers are not allowed throughout the study and must be stopped at least 14 days prior to the first dose of study treatment.
- GS inhibitors; Anti-Notch antibody therapy; and Gastric bypass, lap band, or other gastric procedures that would alter absorption.
 - No prior use, therapy or procedure is allowed; and
 - Not allowed throughout the duration of the treatment period.
- Delivery of nirogacestat via nasogastric tube or gastrostomy tube not allowed.

If the study subject needs concomitant medications or treatment not allowed while on this study, then the Protocol Director will require the subject to stop study treatment. An EOT visit (and EOT assessments) will be done within 30 days of last treatment \pm 7 days. See Section 3.5 (Treatment Period and Duration), Section 5 (Treatment Plan), and Section 6 (Study Procedures and Assessments).

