Secondary Endpoints	
 1. Clinical benefit rate (CR + PR + SD) at 1 year from treatment start with nirogacestat. Response will be assessed according to mRECIST. 2. Median progression free survival will be determined radiographically using RECIST v1.1, mRECIST and volumetrically (change in tumor volume as assessed by MRI volumetric). 3. Objective response rate at 1 year (RECIST v1.1, mRECIST and MRI volumetric); the percentage of subjects who start study treatment and achieve an objective response (CR or PR), will be calculated. 4. Time to response (RECIST v1.1, mRECIST and MRI volumetric) 5. Duration of response (RECIST v1.1, mRECIST and MRI volumetric) 6. AEs will be tabulated with frequencies and percentages for grade, severity, status, and relationship to study drug or study procedure. Assessment will be from time of consent until 30 days after the last treatment.
Exploratory Endpoint	
 • Changes from baseline in patient-reported outcomes (EQ-5D-3L)
Indication	Desmoid tumor
Sample Size	Up to 23 enrolled subjects, to achieve 20 evaluable subjects
Eligibility Criteria	Due to length, the Eligibility Criteria are only presented in one instance. Eligible subjects will be subjects \geq 18 years of age with progressive or symptomatic desmoid tumor that is at least 50% but less than 75% treatable with cryoablation. See Section 3, Subject Selection.
Dose	Nirogacestat 150 mg po BID (150 mg twice-daily) One cycle of treatment = 28 days.
Treatment and Procedural Summary	
 1. Nirogacestat 150 mg by mouth twice-daily continuously for Cycles 1 through 3. 2. Cryoablation procedure (single session) of one tumor mass between Cycles 3 and 4 of nirogacestat treatment. 3. Continued treatment with nirogacestat for Cycles 4 through 26. Treatment with nirogacestat may continue via this study protocol for up to 24 months (26 cycles of treatment), unless there is progression of disease, intolerance, start of new anticancer therapy (as defined in Sections 5.7.2 and 5.7.3), or one of the criteria in Section 3.7 (Subject Study Completion or Termination) occurs. 4. After 24 months of treatment, if clinically indicated, a subject may transition to commercial nirogacestat supply, once the subject has completed the End of Treatment (EOT) visit and is off study.

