1.2. Background

1.2.1. Study Disease

Desmoid tumor is a non-metastasizing but locally aggressive neoplasm that can occur anywhere throughout the body. Desmoids are rare with an estimated incidence in the general population of 2 to 4 per million population per year.² Affected populations can occur in any age group, most commonly seen between the ages of 15 to 60, with a slight preponderance among women than men. Affected locations can include upper and lower extremities, trunk, head and neck region, abdominal wall, and intra-abdominal. The natural history of desmoid is extremely

variable and there are some tumors that spontaneously regress, some that remain stable for years, and some that have unrelenting growth. Tumors that occur intra-abdominally and are associated with familial adenomatous polyposis (FAP) tend to be multi-focal, more aggressive, and potentially fatal. Under histologic exam, desmoid tumors appear as spindle cells in an abundant fibrous stroma with low cellularity, few mitotic figures, and absent necrosis. Staining for nuclear beta-catenin is commonly seen and a fair amount of desmoids have mutations in Catenin Beta 1 (CTNNB1). Other mutations seen are adenomatous polyposis coli (APC) mutations, which are found in FAP patients.

For growing desmoid tumors, options include surgical resection (which can be morbid and has a high recurrence rate), radiation therapy, systemic therapy [such as chemotherapy or vascular endothelial growth factor receptor tyrosine kinase inhibitors (VEGF-TKIs)], and more recently, ablation procedures, such as cryoablation or high intensity focused ultrasound (HIFU).

However, each approach has its pros and cons. For radiation therapy, local control rates are excellent, with approximately 80% at 3 years, however, there are potentially devastating albeit rare long-term side effects such as secondary malignancies.³ For systemic therapy, the time to response is longer (sorafenib trial median of 9 months), and there is associated systemic toxicity. Chemotherapy (doxil, methotrexate/vinblastine) have higher response rates and faster time to response; however, they have more significant side effects than TKIs. For ablation procedures, it may not be technically feasible to totally treat the tumor due to proximity to critical structures such as nerve and skin, there is often a need for multiple treatment sessions. Tumor recurrence or progression is inevitable for tumors that cannot be completely ablated.

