2.1.2. Primary Purpose of the Study

Treatment: The primary purpose of this protocol is treatment. Systemic therapy with oral study agent, nirogacestat, will be given for 3 cycles (1 cycle = 28 days) followed by a single cryoablation procedure between Cycles 3 and 4, and then continued nirogacestat for Cycles 4 through 26. Treatment with nirogacestat may continue via this study for up to 24 months (26 cycles of treatment), unless there is progression of disease, intolerance, subject withdraws their consent, start of a new anticancer therapy (as defined in Section 5.7.2), or until one of the criteria in Section 3.7 (Subject Study Completion or Termination) occurs.

After 24 months of treatment, if clinically indicated, a subject may transition to commercial nirogacestat supply, once the subject has completed the End of Treatment (EOT) visit and is off study.

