
3.1.2. Exclusion Criteria

Prospective Participants Must NOT Meet ANY of These Exclusion Criteria	Yes	No	Supporting Documentation *
1. Participant previously received or is currently receiving therapy with GS inhibitors or anti-Notch antibody therapy.			
2. Participant is currently using any treatment for DT including tyrosine kinase inhibitors (TKIs), NSAIDS (chronic daily use – except as in inclusion criterion 4) or any investigational treatment 28 days (or 5 half-lives, whichever is longer) prior to the first dose of study treatment.			
3. Participant is currently using or anticipates using food or drugs that are known strong or moderate cytochrome P450 3A4 (CYP3A4) inhibitors, or strong CYP3a inducers within 14 days prior to the first dose of study treatment.			
4. Participant has known hypersensitivity to the active substance or to any of the excipients of nirogacestat.			
5. Participant with active or chronic infection at the time of informed consent and during the screening period.			
6. Participant has known malabsorption syndrome or preexisting gastrointestinal condition that may impair absorption of nirogacestat (e.g., gastric bypass, lap band, or other gastric procedures that would alter absorption); delivery of nirogacestat via nasogastric tube or gastrostomy tube is not allowed.			

Prospective Participants Must NOT Meet ANY of These Exclusion Criteria	Yes	No	Supporting Documentation *
7. History of other high-grade malignancy ≤ 2 years previous. Exceptions include prior or concurrent malignancy whose natural history or treatment does not have the potential to interfere with the safety or efficacy assessment of the investigational regimen; adequately treated basal cell or squamous cell skin cancer; or adequately treated, with curative intent, cancer from which the subject is currently in complete remission per study Principal Investigator's (PI's) judgment. Specific situations can be discussed with study PI.			

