10.2. Study Endpoints and Analyses

10.2.1. Primary Endpoint and Analysis

10.2.1.1. Primary Endpoint

The clinical benefit rate (CBR) is defined as the number and proportion of participants who are assessed with either a complete response (CR), a partial response (PR), or stable disease (SD) prior to 1 year after treatment start and show no evidence of loss of response nor progression

within that year. Response and progression will be assessed according to the Revised Response Evaluation Criteria in Solid Tumors (RECIST) v1.1.

10.2.1.2. **Primary Analysis Plan**

The primary analysis will be the calculation of the clinical benefit rate, (CBR), defined as the percentage of subjects in the analysis population who achieve a complete response (CR), partial response (PR), or stable disease (SD) as measured at 12 months \pm 1 month (approximately 1 year) from the start of treatment. CR, PR, and SD are as defined by RECIST v1.1. (See Appendix C RECIST v1.1). The CBR and the two-sided 95% Clopper-Pearson (exact) confidence interval will be calculated.

The analysis population will include all subjects who started nirogacestat and underwent cryoablation. Subjects who withdraw from the study prior to start of treatment or before receiving cryoablation and completing 1 year of treatment will be replaced.

10.2.1.3. **Relevant Subset for Primary Objective and Endpoint**

Evaluable subjects are those subjects who have received cryoablation therapy and completed 1 year of treatment.

10.2.1.4. **Primary Objective and Endpoint Assessment Methods**

CBR will be evaluated on the basis of clinical response as measured using imaging by MRI scan and evaluated by RECIST v1.1 (Appendix C). Determination of response will be made by the treating investigator.

10.2.1.5. **Measurement Time Points for Primary Objective / Outcome**

Imaging will be performed at screening, then every 3 cycles (ie, every 12 weeks \pm 14 days) until End of Treatment. MRI scan will be used at screening and at subsequent time points.

10.2.2. **Secondary Endpoints and Analysis**

10.2.2.1. **Clinical Benefit Rate (CBR) assessed by modified RECIST**

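### Permitted palliative radiation to a target desmoid does not count against the 1-year clinical benefit rate, and 'new anticancer therapy' is defined by a list that omits marketed desmoid drugs

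*Protocol*

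**What the plan says.** Sections 3.1.3 and 5.7.2 list what is prohibited on study. On radiation, 5.7.2 says: "Definitive radiation (treatment with intent to cure) is not allowed. However, palliative radiation is allowed". Neither section limits the site. The instruction at the end of each list, to stop study treatment, applies only to therapy that is not allowed.

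Section 10.2.1.1 defines clinical benefit as CR, PR or "stable disease (SD) prior to 1 year after treatment start and show no evidence of loss of response nor progression" within that year, by RECIST v1.1. Section 2.3.2.1 gives the same rule. Section 10.2.1.2 takes CR, PR or SD at 12 months ± 1 month in everyone who started nirogacestat and was cryoablated. Section 10.2.1.3 calls evaluable only those who were cryoablated and completed 1 year of treatment.

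For other added therapy, Section 2.1.2 and many later sections end nirogacestat at the "start of a new anticancer therapy (as defined in Section 5.7.2"). The synopsis has "start of new anticancer therapy (as defined in Sections 5.7.2 and 5.7.3"). The only general drug category that 5.7.2 names is "Other investigational anti-cancer therapies"; it also names GS inhibitors, anti-Notch antibodies and CYP3A4-active drugs. Section 5.7.3 covers phosphate supplements and palliative-care medication. Other desmoid drugs are barred by exclusion criterion 2 ("Participant is currently using any treatment for DT including tyrosine kinase inhibitors (TKIs), NSAIDS"), which applies before the first dose.

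**The concern.** The trial has one arm, is open label, and is read by the treating investigator (10.2.1.4). No control group receives the same added therapy, so any tumour control it produces is credited to the study regimen. For the clinical benefit rate (CBR) the error can go only upwards: a subject who would otherwise have progressed can become a success, and no success becomes a failure.

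The situation is plausible here. Section 1.2.1 describes desmoid as non-metastasizing, so palliative radiation for this disease goes to a desmoid lesion. Inclusion criterion 1 admits subjects on symptoms alone, so pain without RECIST progression falls within the study population.

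**Working it through.** **1. Tracing one subject through the text (a constructed case, not one the protocol describes).** The target desmoid becomes more painful at month 6, with growth below the 20% RECIST threshold. Palliative radiation is given to it.
- Is nirogacestat stopped? Not by 5.7.2 or 3.1.3: the radiation is allowed, and 5.7.2 is the section that defines new anticancer therapy.
- Is the subject in the analysis? Yes: cryoablated, with 1 year of treatment completed, so both 10.2.1.2 and 10.2.1.3 are met.
- Is the subject a failure? Only if imaging shows otherwise. The test is to "show no evidence of loss of response nor progression", and added therapy is not mentioned.
- Result: SD at month 12 is a primary-endpoint success.

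**2. Tracing a subject who starts a marketed desmoid drug.** Read by its plain words, the stopping rule ends nirogacestat. The subject then misses 1 year of treatment and is not evaluable under 10.2.1.3. Under 10.2.1.2 the same subject stays in the population, and 3.7.2 lets follow-up continue on the study schedule, so a 12-month scan can exist and be scored. Read strictly by the 5.7.2 list, the rule does not name the drug and nirogacestat may continue. On none of these routes does starting the drug make the subject a failure.

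**3. Size per subject.** With N = 20 evaluable (10.4.1), 1/20 = 5 percentage points. Two such subjects would make 14/20 = 70% read as 16/20 = 80%. The planned two-sided 95% Clopper-Pearson lower limit moves from 45.7% (14/20) to 56.3% (16/20), that is, from below the null of 50% to above it.

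**4. The plan's own figures.** Section 10.4.2 states 100.0% power for 0.5 versus 0.8, one-sided exact α = 0.05, N = 20. This was not reproduced. The stated rule of at least 11/20 (10.4.4) has P(X ≥ 11 | 0.8) = 0.997 but P(X ≥ 11 | 0.5) = 0.412. The smallest cut-off that holds α is 15/20, with P(X ≥ 15 | 0.5) = 0.021 and power 0.804. That discrepancy is a separate matter; both cut-offs are shown below only so that the result does not depend on it.

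**5. Effect on a false success.** The protocol gives no rate of added therapy, so a share k of true failures turned into scored benefit is assumed. For an ineffective regimen the scored CBR is p = 0.5 + 0.5k. With 10 expected failures in 20, k = 0.1, 0.2 and 0.3 mean 1, 2 and 3 subjects on average.

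| k (assumed) | scored CBR | P(X ≥ 11) | P(X ≥ 15) |
|---|---|---|---|
| 0 | 0.50 | 0.412 | 0.021 |
| 0.1 | 0.55 | 0.591 | 0.055 |
| 0.2 | 0.60 | 0.755 | 0.126 |
| 0.3 | 0.65 | 0.878 | 0.245 |

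The row k = 0 is what remains if added therapy is counted as non-benefit.

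**The case against.** Several stronger readings are tempting, and the protocol does not support them.

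- *Marketed desmoid drugs are freely allowed and their users are scored as successes.* A reader might infer this from the 5.7.2 list. But the stopping rule recurs throughout the protocol and plausibly covers such drugs, so the subject may be dropped as non-evaluable. Scored benefit is one possible result, not the certain one.
- *Repeat cryoablation is an open rescue.* Section 5.3 calls cryoablation standard of care, but the same section and 4.2 and 5.2 specify a single session.
- *An irradiated subject will probably read as stable.* Section 1.2.1 says "For radiation therapy, local control rates are excellent, with approximately 80% at 3 years", but that is for radiation in general, and definitive radiation is barred. The protocol gives no control rate for palliative radiation.
- *Palliative radiation always goes to the target lesion.* Disease can be multifocal and only one mass is ablated, so this is possible, not established.
- *PFS, ORR, time to response and duration of response are defective for lacking a rule.* Handling of scans and censoring after added therapy can sit in a statistical analysis plan that is not shown.

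It can also be said that such cases may be rare. Section 1.2.4 reports no progressive disease among 16 evaluable desmoid subjects on nirogacestat. RECIST progression before the added therapy already counts as failure. The 14-versus-16 example passes the stated cut-off of 11 either way. All of this stands and limits the size. It does not remove the primary-endpoint gap, because the permission and the failure criterion are both stated in the protocol, and following them gives the result in step 1. Appendix C's remark on lesions with prior local treatment concerns measurability at baseline and does not make the subject a failure.

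**Conclusion.** The point holds in two parts. First, as written, a target desmoid irradiated with palliative intent before RECIST progression and stable at 12 months is a primary-endpoint success. This is a stated rule that favours the regimen in a single-arm trial. Second, the definition of new anticancer therapy refers to sections that do not name marketed desmoid drugs, so the fate of a subject who starts one is undetermined: excluded, or scored on imaging, but not a failure on that ground.

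The size is 5 percentage points of CBR per affected subject. How many there will be is unknown and may be none; the false-success probabilities above rest entirely on the assumed 10 to 30% conversion. The point should be corrected before the primary analysis, but with the frequency unknown it does not by itself undermine the trial.

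**What to change.** - In 10.2.1.1 and 10.2.1.2, and to match in 2.3.2.1, state that a subject who receives non-protocol therapy directed at a target desmoid lesion (radiation of any intent, surgery) or any non-protocol systemic anti-desmoid drug before the 1-year assessment stays in the denominator and counts as not having clinical benefit. Align 10.2.1.3 so that stopping for such therapy does not remove the subject.
- Report the imaging-only CBR as a sensitivity analysis.
- Record the date and site of any such therapy on the CRF.
- Apply a consistent rule to PFS and the response endpoints, here or in the statistical analysis plan.
- Define new anticancer therapy explicitly and reconcile 3.1.3, 5.7.2, 5.7.3 and the synopsis. Which therapies are permitted is for the sponsor to decide; no view is taken here.

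Cost: a few sentences and one CRF field, with no extra visits or subjects. The CBR may be slightly less favourable. If the rule lowered the expected rate from 0.80 to 0.75 or 0.70 (assumed), power would be 98.6% or 95.2% with the 11/20 cut-off, and 61.7% or 41.6% with 15/20, against 99.7% and 80.4% at 0.80.

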3.1.3. Lifestyle Considerations

Nirogacestat may be taken with or without food. Tablets should be swallowed whole and should not be chewed prior to swallowing. Tablets should not be ingested if broken, cracked, or not fully intact. Doses should be taken by mouth TWICE per day, approximately every 12 hours.

If a participant misses a scheduled dose of study treatment, and it is within 6 hours of the scheduled dose, the participant should immediately administer the missed dose and resume study treatment in accordance with the normal administration schedule. If more than 6 hours have elapsed since the time of schedule administration, the participant should be instructed not to administer the missed dose and to resume study treatment as prescribed.

Participants should not take 2 doses together to “make up” for a missed dose.

If a participant vomits any time after taking a dose, then they must be instructed not to take another dose to “make up” for vomiting, but rather to resume subsequent doses as prescribed.

If a participant inadvertently takes 1 extra dose then the participant should not take the next scheduled dose of study treatment.

Delivery of nirogacestat via nasogastric tube or gastrostomy tube is not allowed.

Nirogacestat has not been reported to cause dizziness or hypotension in clinical studies. However, as nirogacestat remains under evaluation, subjects should be instructed that if they experience dizziness, they should avoid potentially hazardous tasks such as driving or operating machinery.

Participants should consult their study doctor before taking any new medications, over-the-counter drugs, or supplements.

Concomitant Medications to Avoid:

See also Section 4 (Study Intervention), and Section 5.8 (Concomitant Medications, Procedures, and Supportive Care Guidelines), and Section 7.3 (Potential Adverse Events and Risks).

Please also refer to the current Investigator’s Brochure and the Ogsiveo™ (nirogacestat) package insert for detailed information regarding medications to avoid taking with nirogacestat.

During this study, participants are asked to avoid the following medications, foods, and supplements during their treatment on this study:

- Participants must refrain from consuming Seville oranges, grapefruit or grapefruit juice, pomelos, exotic citrus fruits, or grapefruit hybrids at least 14 days prior to the first dose of study treatment and throughout the study.
- CYP3A4 substrates with a narrow therapeutic index

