- The choice of anti-emetic drug(s) and anti-diarrheal drug(s), as well as the duration of treatment, is up to the investigator assuming there is no known or expected drug-drug

interaction (DDI). See Section 5.6 (Dose Modifications; select AE management recommendations, diarrhea).

Prohibited Concomitant Medications and Treatment (while on this study)

- Other investigational cancer therapies
- Anti-cancer surgery
- Definitive radiation (treatment with intent to cure) is not allowed. However, palliative radiation is allowed.
- Strong CYP3A4 inhibitors and strong CYP3A4 inducers are not allowed throughout the study and must be stopped at least 14 days prior to the first dose of study treatment.
 - Because inhibition of CYP3A4 isoenzymes may increase nirogacestat exposure leading to potential increases in toxicities, the use of known strong CYP3A4 inhibitors is not allowed throughout the study and must be stopped at least 14 days prior to the first dose of study treatment.
 - Nirogacestat metabolism may be induced when taking strong CYP3A4 inducers resulting in reduced plasma concentrations. Therefore, co-administration of nirogacestat in combination with strong CYP3A4 inducers is not allowed throughout the study and must be stopped at least 14 days prior to the first dose of study treatment.
- GS inhibitors; anti-notch antibody therapy; and gastric bypass, lap band, or other gastric procedures that would alter absorption.
 - No prior use, therapy or procedure is allowed; and
 - Not allowed throughout the duration of the treatment period.
- Delivery of nirogacestat via nasogastric tube or gastrostomy tube not allowed

If the study subject needs concomitant medications or treatment not allowed while on this study, then the Protocol Director will require the subject to stop study treatment. An EOT visit (and EOT assessments) will be done within 30 days of last treatment \pm 7 days. See Section 3.5 (Treatment Period and Duration), Section 5 (Treatment Plan), and Section 6 (Study Procedures and Assessments).

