3.7.2. Investigator-initiated Discontinuation of Study Treatment

The investigator may require a study subject to discontinue study treatment in the event of one of the following:

- The study subject has disease progression.
- Noncompliance
- The study subject needs treatment not allowed in the study.
- Pregnancy

- The study subject develops an AE that cannot be tolerated or that cannot be controlled with other medication.
- The investigator feels that it is in subject's best interest to stop treatment.
- The study subject is unable to meet study requirements.
- New information about the treatment of desmoid tumor becomes available.

If study therapy is stopped but the study subject allows the physician to submit follow up information, subject will continue to be followed clinically according to the study schedule.

If a subject must be removed from the study, the reason for the study removal and the date the subject was removed will be documented in the subject documentation/Case Report Form (CRF).

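### Sections 1.3.1 and 7.3.1 let nirogacestat be held and resumed around an unavoidable CYP3A4 drug, Section 5.7.2 orders a stop with an End of Treatment visit, and the 3.1.3 prohibited list omits moderate inhibitors

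*Protocol*

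**What the plan says.** **Prohibited drugs.** Section 5.7.2 says that "Strong and moderate CYP3A4 inhibitors and strong CYP3A4 inducers are not allowed throughout the study". The corresponding list in Section 3.1.3 says that "Strong CYP3A4 inhibitors and strong CYP3A4 inducers are not allowed throughout the study", and its explanatory sub-bullet again names only the strong class: "the use of known strong CYP3A4 inhibitors is not allowed throughout the study". Exclusion criterion 3 (Section 3.1.2) covers strong and moderate inhibitors and strong inducers, in line with 5.7.2.

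**What happens if such a drug is needed.** Sections 5.7.2 and 3.1.3 carry the same paragraph. If a subject needs a medication or treatment that the study does not allow, "then the Protocol Director will require the subject to stop study treatment", and an EOT visit with EOT assessments follows. Neither section mentions resumption.

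The drug-interaction text in Sections 1.3.1 and 7.3.1 says otherwise. For an unavoidable strong or moderate inhibitor, nirogacestat is interrupted at once and stays off while the inhibitor is given. It may restart one week after a strong inhibitor ends, or immediately after a moderate one ends. For a required strong inducer, nirogacestat may be interrupted and may restart as soon as the inducer ends.

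**The concern.** For one clinical event the protocol gives two instructions that cannot both be followed: pause and resume, or stop and perform the EOT visit. The event is foreseeable. Appendix F lists aprepitant, erythromycin, fluconazole, verapamil and diltiazem as intermediate-strength inhibitors. Infection is a listed risk of cryoablation, and nausea and vomiting are among the common nirogacestat adverse events.

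Two things are at stake. The first is conduct: whether a subject keeps an active drug after a short course of another medicine should not depend on which section the treating team opens. The second is the evaluable set. Under 10.2.1.3 a subject must have had cryoablation and completed 1 year of treatment. A short hold need not cost a subject that status, but a stop before one year does. Enrolment is capped at 23 to yield 20 evaluable subjects, which leaves 23 − 20 = 3 to spare.

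**Working it through.** The protocol states no figure on this point and no arithmetic decides it, so the check compares the texts.

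| Drug needed | 1.3.1 and 7.3.1 | 5.7.2 | 3.1.3 prohibited list and stop paragraph |
|---|---|---|---|
| Strong inhibitor | Interrupt; may resume one week after it ends | Barred; stop, EOT visit | Barred; stop, EOT visit |
| Moderate inhibitor | Interrupt; may resume when it ends | Barred; stop, EOT visit | Not named in the list |
| Strong inducer | May interrupt; may resume when it ends | Barred; stop, EOT visit | Barred; stop, EOT visit |

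1. **Hold or stop.** In every row the second and third columns give different outcomes for the same drug. For strong inhibitors and strong inducers, 3.1.3 adds a second statement of the stop rule.

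2. **Does any text rank them?** 3.1.3 refers the reader to 7.3. The drug-interaction text in 7.3.1 refers to 3.1.3, 1.3 and Appendix F, and that in 1.3.1 refers to 3.1.3 and 7.3. Section 5.7.2 refers to 3.1.3. The sections point at one another, and none says which prevails.

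3. **Are moderate inhibitors allowed through 3.1.3?** No. Section 5.7 reads "No restrictions on supportive care, except as noted in Section 3.1.3. (Lifestyle Considerations" and goes on to name 5.7.1, 5.7.2 and 5.7.3, so the restrictions apply together and 5.7.2 bars moderate inhibitors. Exclusion criterion 3, 1.3.1 and 7.3.1 also treat them as drugs to keep away from. The 3.1.3 list is the outlier.

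4. **Link to evaluability.** A resumed subject can go on to complete a year of treatment and meet 10.2.1.3. A subject stopped before one year cannot.

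**The case against.** The strongest reply is that 1.3.1 and 7.3.1 are risk sections carrying modified Investigator's Brochure text, whereas Section 5 is the treatment plan and should govern. That is a reasonable guess at intent. However, those sections also give study-specific instructions, such as the 14-day washout before the first study dose, and 3.1.3 sends the reader to 7.3.

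It can also be said that stopping need not be final. Table 4 and Appendix G say outright when discontinuation is permanent, while 5.7.4 uses stop for an overdose and then leaves interruption or modification to the investigator. This stands in part: permanence in 5.7.2 is inferred. The attached EOT visit makes it the natural reading, and if a pause was meant the text needs to say so.

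The trial has a single centre and 5.7.2 assigns the decision to one Protocol Director, which limits inconsistent handling. That is fair, but it does not tell that person which rule to apply.

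A reader might take Section 3.7.2 as a third rule, because it says "The investigator may require a study subject to discontinue study treatment in the event of one of the following" and lists the case where "The study subject needs treatment not allowed in the study". The documents do not support this. It is a general list of powers that also covers pregnancy, for which 5.6 gives its own direction, so its permissive verb does not soften specific rules elsewhere.

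**Conclusion.** The conflict between hold-and-resume and stop-with-EOT is real, stands in the current body text and is not settled anywhere in the protocol. The 3.1.3 list is incomplete on moderate inhibitors.

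Three stronger readings should not be drawn:

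- **That 3.1.3 permits moderate inhibitors.** It does not, because 5.7 and 5.7.2 keep them barred.
- **That the pointer in 3.1.3 to "Section 5.8 (Concomitant Medications, Procedures, and Supportive Care Guidelines") leaves a gap.** The contents list for Section 5 ends at 5.7, and the title printed with the pointer matches 5.7. This is a clerical numbering slip.
- **That a given amount of treatment or clinical benefit would be lost.** Any such figure would need an assumed length of drug course and an assumed cycle of stopping, and the protocol gives neither these nor a frequency of use.

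The effect on the clinical benefit rate is therefore unquantified and probably small. What correction buys is one consistent rule on drug exposure and discontinuation, and no needless loss of subjects who must complete 1 year of treatment to be evaluable. The conclusion assumes that stopping with an EOT visit means discontinuation.

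**What to change.** (a) In both inhibitor bullets of the 3.1.3 prohibited list, change *strong* to *strong and moderate*. Correct the section number of the cross-reference to 5.7 in the same edit.

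(b) After the stop paragraph in 5.7.2 and in 3.1.3, add: *Exception: for unavoidable temporary use of a strong or moderate CYP3A4 inhibitor or a strong CYP3A4 inducer, nirogacestat is interrupted and may be resumed as stated in 1.3.1 and 7.3.1.*

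The document does not show which rule the sponsor intended. If a mandatory permanent stop is meant, replace (b) with a sentence in 1.3.1 and 7.3.1 saying that 5.7.2 governs in this study; the Brochure-derived guidance can then stay as background.

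The cost is amendment wording in 3.1.3 and 5.7.2, or in 3.1.3, 1.3.1 and 7.3.1 under the alternative. Design, sample size and analysis do not change.
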